10.7. Appendix 7: Abbreviations and Definitions

Term	Definition
Aβ	amyloid beta
abuse	Use of a study intervention for recreational purposes or to maintain an addiction or dependence
AD	Alzheimer's disease
ADA	anti-drug antibody
AE	adverse event
ALP	Alkaline phosphatase
ALT	alanine aminotransferase
ApoE4	apolipoprotein E genotype ε4
ARIA	amyloid-related imaging abnormalities
ARIA-E	amyloid-related imaging abnormality–edema/effusions
ARIA-H	amyloid-related imaging abnormality–hemorrhage/hemosiderin deposition
AST	aspartate aminotransferase
blinding/masking	A single-blind study is one in which the investigator and/or the investigator's staff are aware of the treatment but the participant is not, or vice versa, or when the sponsor is aware of the treatment but the investigator and/or the investigator's staff and the participant are not. A double-blind study is one in which neither the participant nor any of the investigator or sponsor staff who are involved in the treatment or clinical evaluation of the subjects are aware of the treatment received.
BMI	body mass index
CFR	Code of Federal Regulations
complaint	A complaint is any written, electronic, or oral communication that alleges deficiencies related to the identity, quality, purity, durability, reliability, safety or effectiveness, or performance of a drug or drug delivery system.
compliance	Adherence to all study-related, good clinical practice (GCP), and applicable regulatory requirements.
CRF	case report form; a printed, optical, or electronic document designed to record all of the protocol-required information to be reported to the sponsor for each trial participant.

CRP	clinical research physician: Individual responsible for the medical conduct of the study. Responsibilities of the CRP may be performed by a physician, clinical research scientist, global safety physician or other medical officer.
CRU	clinical research unit
ECG	electrocardiogram
EDC	electronic data capture system
enroll	The act of assigning a participant to a treatment. Participants who are enrolled in the study are those who have been assigned to a treatment.
enter	Participants entered into a study are those who sign the informed consent form directly or through their legally acceptable representatives.
GCP	good clinical practice
HIV	Human immunodeficiency virus
I5T-MC-AACC	AACC
I5T-MC-AACD	AACD
I5T-MC-AACG	AACG
I5T-MC-AACK	AACK
IB	Investigator's Brochure
ICF	informed consent form
ICH	International Council for Harmonisation
IEC	Independent Ethics Committee
Ig	immunoglobulin
IMP	Investigational Medicinal Product (see also "investigational product") A medicinal product which is being tested or used as a reference, including as a placebo, in a clinical trial.
informed consent	A process by which a participant voluntarily confirms their willingness to participate in a particular study, after having been informed of all aspects of the study that are relevant to the participant's decision to participate. Informed consent is documented by means of a written, signed and dated informed consent form.
interim analysis	An interim analysis is an analysis of clinical study data, separated into treatment groups, that is conducted before the final reporting database is created/locked.

investigational product	A pharmaceutical form of an active ingredient or placebo being tested or used as a reference in a clinical trial, including products already on the market when used or assembled (formulated or packaged) in a way different from the authorized form, or marketed products used for an unauthorized indication, or marketed products used to gain further information about the authorized form.
IRB	Institutional Review Board
IRR	infusion-related reactions
IV	intravenous
Lilly	Eli Lilly and Company
MCI	mild cognitive impairment
participant	Equivalent to CDISC term “subject”: an individual who participates in a clinical trial, either as recipient of an investigational medicinal product or as a control
PC	product complaint
PK	pharmacokinetics\
SAE	serious adverse event
SAP	statistical analysis plan
screen	The act of determining if an individual meets minimum requirements to become part of a pool of potential candidates for participation in a clinical study.
SoA	Schedule of Activities
TBL	total bilirubin
TEAE	Treatment-emergent adverse event: An untoward medical occurrence that emerges during a defined treatment period, having been absent pretreatment, or worsens relative to the pretreatment state, and does not necessarily have to have a causal relationship with this treatment.
TE-ADA	treatment-emergent anti-drug antibodies

11. References

## 2. ABBREVIATIONS

Abbreviations pertain to the Statistical Analysis Plan (SAP) only (not the tables, figures and listings [TFLs]).

%AUC( $t_{last}-\infty$ )	Percentage of AUC(0- $\infty$ ) extrapolated
AE	Adverse event
ADA	Anti-drug antibody
AUC	Area under the concentration versus time curve
AUC(0- $\infty$ )	Area under the concentration versus time curve from time zero to infinity
AUC(0- $t_{last}$ )	Area under the concentration versus time curve from time zero to time $t$ , where $t$ is the last time point with a measurable concentration
BQL	Below the lower limit of quantitation
$C_{last}$	Last quantifiable drug concentration
$C_{max}$	Maximum observed drug concentration
CI	Confidence interval
CL/F	Apparent total body clearance of drug calculated after extra-vascular administration
CRF	Case Report Form
CRU	Clinical Research Unit
CSR	Clinical Study Report
CV	Coefficient of variation
ECG	Electrocardiogram
ICH	International Conference on Harmonisation
IV	Intravenous
MedDRA	Medical Dictionary for Regulatory Activities
PK	Pharmacokinetic
SAP	Statistical Analysis Plan
SD	Standard deviation
SOP	Standard Operating Procedure
TFLs	Tables, Figures, and Listings
$t_{1/2}$	Half-life associated with the terminal rate constant ( $\lambda_z$ ) in non-compartmental analysis
$t_{max}$	Time of maximum observed drug concentration

---

$V_{ss}$	Volume of distribution at steady state following intravenous administration
$V_z$	Volume of distribution during the terminal phase after intravenous administration

### **3. INTRODUCTION**

This SAP has been developed after review of the Clinical Study Protocol (final version dated 11 Jan 2022) and protocol amendment (a) dated 17 Jun 2022.

This SAP describes the planned analysis of the safety, tolerability and pharmacokinetic (PK) data from this study. A detailed description of the planned TFLs to be presented in the clinical study report (CSR) is provided in the accompanying TFL shell document.

The intent of this document is to provide guidance for the statistical and PK analyses of data. In general, the analyses are based on information from the protocol, unless they have been modified by agreement with Eli Lilly and Company. A limited amount of information concerning this study (e.g., objectives, study design) is given to help the reader's interpretation. This SAP must be finalized prior to unblinding. When the SAP and TFL shells are agreed upon and finalized, they will serve as the template for this study's CSR.

This SAP supersedes the statistical considerations identified in the protocol; where considerations are substantially different, they will be so identified. If additional analyses are required to supplement the planned analyses described in this SAP, they may be performed and will be identified in the CSR. Any substantial deviations from this SAP will be agreed upon with Eli Lilly and Company and identified in the CSR. Any minor deviations from the TFLs may not be documented in the CSR.

This SAP is written with consideration of the recommendations outlined in the International Conference on Harmonisation (ICH) E9 Guideline entitled Guidance for Industry: Statistical Principles for Clinical Trials and the ICH E3 Guideline entitled Guidance for Industry: Structure and Content of Clinical Study Reports.

#### 4. STUDY OBJECTIVES AND ENDPOINTS

Objectives	Endpoints
Primary	

To investigate the safety and tolerability of donanemab versus placebo following single dose intravenous (IV) administration in healthy Chinese participants

	

Incidence of treatment-emergent adverse events (TEAE), serious adverse events (SAE)

Secondary	

To characterize the pharmacokinetic profile of donanemab following single dose IV administration in healthy Chinese participants

	

Maximum observed drug concentration (<math>C_{max}</math>) and area under the concentration versus time curve from time zero to infinity (<math>AUC_{0-\infty}</math>)

Exploratory	

To characterize immunogenicity of donanemab following single dose IV administration in healthy Chinese participants

	

Incidence of treatment-emergent anti-drug antibodies (TE-ADA)

#### 5. STUDY DESIGN

This is a parallel treatment, Phase 1, participant- and investigator-blind, placebo-controlled, randomized study to evaluate the safety, tolerability, and PK of a single IV dose of donanemab in healthy Chinese participants. This study will be conducted in China. Up to 36 participants may be enrolled so that approximately 30 participants complete the study.

The study will include 3 cohorts, each with 12 participants randomized in a 5 (donanemab): 1 (placebo) ratio.

The planned doses are:

- Cohort 1: 350 mg IV single dose
- Cohort 2: 700 mg IV single dose
- Cohort 3: 1400 mg IV single dose

#### Screening Period

Screening may occur up to 28 days prior to randomization and dosing with study intervention. Once the informed consent is signed by the participants, they will be assessed for eligibility and will undergo screening procedures.

Participants who are not enrolled within 28 days of screening may undergo an additional medical assessment and/or clinical measurements to confirm their eligibility. In such instances, the following screening tests and procedures may be repeated: vital signs and clinical laboratory tests.

## Inpatient Period

Eligible participants will be admitted to the clinical research unit (CRU) on Day -1 prior to dosing with study intervention. On Day 1, participants will be dosed with a single IV dose of donanemab or placebo. Participant will be discharged on Day 5 at the discretion of the investigator and after completion of all assessments. Participants will be monitored for safety and PK, and immunogenicity samples will be collected.

## Follow-up Period

After discharge from the CRU, participants will be required to visit the CRU on an outpatient basis. The follow-up period will be 12 weeks  $\pm$  7 days after completion of dosing or until early discontinuation.

## 6. BLINDING

This is a randomized participant- and investigator-blind study. All measures possible must be taken to maintain the blind; access to the blinding information will be restricted to authorized personnel as described in the protocol. All study site personnel, except staff who prepare the study intervention, will be blinded to treatment allocation.

In case of an emergency, the investigator has the sole responsibility for determining if unblinding of a participant's treatment assignment is warranted for medical management of the event. In such cases, the unblinding is to be conducted according to the protocol.

The Labcorp biometrics and Eli Lilly study teams will be unblinded throughout the study.

## 7. TREATMENTS

The following is a list of the study treatment abbreviations that will be used in the TFLs.

Cohort	Study Treatment Name	Treatment order in TFL
1 to 3	Placebo IV	1
1	350 mg Donanemab IV	2
2	700 mg Donanemab IV	3
3	1400 mg Donanemab IV	4

Abbreviations: IV = intravenous

## 8. SAMPLE SIZE JUSTIFICATION

Approximately 36 participants may be enrolled in 3 dosing cohorts. The sample sizes described are customary for Phase 1 studies evaluating safety and PK parameters and is not powered on the basis of statistical hypothesis testing. Each cohort will comprise approximately 12 participants with a randomization ratio of 5:1 between donanemab and placebo. Participants who discontinue the study before completing may be replaced at the discretion of the sponsor and investigator. The replacement participant can complete the entire study period.

## **9. DEFINITION OF ANALYSIS POPULATIONS**

The “Entered” population will consist of all participants who sign the informed consent form.

The “Safety” population will consist of all participants randomly assigned to study intervention and who take at least 1 dose of study intervention. Participants will be analyzed according to the intervention they actually received.

The “Pharmacokinetic” population will consist of all enrolled participants who received at least 1 full dose of donanemab and have baseline and at least 1 postbaseline evaluable PK sample. Participants will be analyzed according to the intervention they actually received.

All protocol deviations that occur during the study will be considered for their severity/impact and will be taken into consideration when participants are assigned to analysis populations.

## **10. STATISTICAL METHODOLOGY**

### **10.1 General**

Data listings will be provided for all data that is databased. Summary statistics and statistical analysis will only be presented for data where detailed in this SAP. For continuous data, summary statistics will include the arithmetic mean, arithmetic standard deviation (SD), median, minimum, maximum and n; for log-normal data (e.g. the PK parameters: area under the concentration versus time curve [AUC] and  $C_{max}$ ) the geometric mean and geometric coefficient of variation (CV%) will also be presented. For categorical data, frequency count and percentages will be presented. Data listings will be provided for all participants up to the point of withdrawal, with any participants excluded from the relevant population highlighted. Summary statistics and statistical analyses will generally only be performed for participants included in the relevant analysis population. For the calculation of summary statistics and statistical analysis, unrounded data will be used.

For change from baseline summary statistics, each individual change from baseline will be calculated by subtracting the individual participant’s baseline value from the value at that timepoint. The individual participant’s change from baseline values will be used to calculate the summary statistics (arithmetic mean, arithmetic SD, median, minimum, maximum and number of observations) using a SAS procedure such as Proc Univariate.

Data analysis will be performed using SAS® Version 9.4 or greater.

### **10.2 Demographics and Participant Disposition**

Participant disposition will be listed. The demographic variables age, sex, race, ethnicity, country of enrolment, site ID, body weight, height and body mass index will be summarized and listed. All other demographic variables will be listed only.

## 10.3 Pharmacokinetic Assessment

### 10.3.1 Pharmacokinetic Analysis

Noncompartmental methods applied with a validated software program (Phoenix WinNonlin Version 8.1.1 or later) to the serum concentrations of donanemab will be used to determine the following PK parameters, when possible:

Parameter	Units a	Definition
AUC(0-t last )	h*ng/mL	area under the concentration versus time curve from time zero to time t, where t is the last time point with a measurable concentration
AUC(0-∞)	h*ng/mL	area under the concentration versus time curve from time zero to infinity b
%AUC(t last -∞)	%	percentage of AUC(0-∞) extrapolated
C max	ng/mL	maximum observed drug concentration
t max	h	time of maximum observed drug concentration
t 1/2	h	half-life associated with the terminal rate constant ( $\lambda_z$ ) in non-compartmental analysis
CL	L/h	total body clearance of drug calculated after intravenous administration
V z	L	volume of distribution during the terminal phase after intravenous administration
V ss	L	volume of distribution at steady state following intravenous administration

aUnits are based on concentration units (provided by the bioanalytical lab or preferred units for presentation of PK parameters) and dose units used in the study.

bBased on the last observed quantifiable concentration

Additional PK parameters may be calculated, as appropriate.

Exploratory graphical analyses relating donanemab serum exposure and immunogenicity may be conducted.

The software and version used for the final analyses will be specified in the CSR. Any exceptions or special handling of data will be clearly documented within the final CSR.

Formatting of tables, figures and abbreviations will follow the Eli Lilly Global PK/PD/TS Tool: NON-COMPARTMENTAL PHARMACOKINETIC STYLE GUIDE. The version of the tool effective at the time of PK analysis will be followed.

### General PK Parameter Rules

- Actual sampling times will be used in the final analyses of individual PK parameters, except for non-bolus pre-dose sampling times which will be set to zero.

- $C_{\max}$  and  $t_{\max}$  will be reported from observed values. If  $C_{\max}$  occurs at more than one time point,  $t_{\max}$  will be assigned to the first occurrence of  $C_{\max}$ .
- AUC parameters will be calculated using a combination of the linear and logarithmic trapezoidal methods (linear-log trapezoidal rule). The linear trapezoidal method will be applied up to  $t_{\max}$  and then the logarithmic trapezoidal method will be used after  $t_{\max}$ . The minimum requirement for the calculation of AUC will be the inclusion of at least 3 consecutive serum concentrations above the lower limit of quantitation, with at least 1 of these concentrations following  $C_{\max}$ .
- AUC(0-∞) values where the percentage of the total area extrapolated is more than 20% will be flagged. Any AUC(0-∞) value excluded from summary statistics will be noted in the footnote of the summary table.
- Half-life ( $t_{1/2}$ ) will be calculated, when appropriate, based on the apparent terminal log-linear portion of the concentration-time curve. The start of the terminal elimination phase for each participant will be defined by visual inspection and generally will be the first point at which there is no systematic deviation from the log-linear decline in serum concentrations. Half-life will only be calculated when a reliable estimate for this parameter can be obtained comprising of at least 3 data points. If  $t_{1/2}$  is estimated over a time window of less than 2 half-lives, the values will be flagged in the data listings. Any  $t_{1/2}$  value excluded from summary statistics will be documented in the footnote of the summary table.
- A uniform weighting scheme will be used in the regression analysis of the terminal log-linear portion of the concentration-time curve.
- The parameters based on predicted last quantifiable drug concentration ( $C_{\text{last}}$ ) will be reported.

### Individual PK Parameter Rules

- Only quantifiable concentrations will be used to calculate PK parameters with the exception of special handling of certain concentrations reported below the lower limit of quantitation (BQL). Serum concentrations reported as BQL will be set to a value of zero when all of the following conditions are met:
  - The compound is non-endogenous.
  - The samples are from the initial dose period for a participant or from a subsequent dose period following a suitable wash-out period.
  - The time points occur before the first quantifiable concentration.
- All other BQL concentrations that do not meet the above criteria will be set to missing.
- Also, where 2 or more consecutive concentrations are BQL towards the end of a profile, the profile will be deemed to have terminated and therefore any further quantifiable

concentrations will be set to missing for the calculation of the PK parameters unless it is considered to be a true characteristic of the profile of the drug.

### Individual Concentration vs. Time Profiles

- Individual concentrations will be plotted utilizing actual sampling times.
- The terminal point selections will be indicated on a semi-logarithmic plot.

### Average Concentration vs. Time Profiles

- The average concentration profiles will be graphed using scheduled (nominal) sampling times.
- The average concentration profiles will be graphed using arithmetic average concentrations.
- The pre-dose average concentration for single-dose data from non-endogenous compounds will be set to zero. Otherwise, only quantifiable concentrations will be used to calculate average concentrations.
- Concentrations at a sampling time exceeding the sampling time window specified in the protocol, or  $\pm 10\%$ , will be excluded from the average concentration profiles.
- Concentrations excluded from the mean calculation will be documented in the final CSR.
- A concentration average will be plotted for a given sampling time only if 2/3 of the individual data at the time point have quantifiable measurements that are within the sampling time window specified in the protocol or  $\pm 10\%$ . An average concentration estimated with less than 2/3 but more than 3 data points may be displayed on the mean concentration plot if determined to be appropriate and will be documented within the final CSR.

### Treatment of Outliers during PK Analysis

Application of this procedure to all PK analyses is not a requirement. Rather, this procedure provides justification for exclusion of data when scientifically appropriate. This procedure describes the methodology for identifying an individual value as an outlier for potential exclusion, but does not require that the value be excluded from analysis. The following methodology will not be used to exclude complete profiles from analysis.

#### Data within an Individual Profile

A value within an individual profile may be excluded from analysis if any of the following criteria are met:

- For PK profiles during single dosing of non-endogenous compounds, the concentration in a pre-dose sample is quantifiable.
- For any questionable datum that does not satisfy the above criteria, the profile will be evaluated and results reported with and without the suspected datum.

#### Data between Individual Profiles

1. If  $n < 6$ , then the dataset is too small to conduct a reliable range test. Data will be analyzed with and without the atypical value, and both sets of results will be reported.
2. If  $n \geq 6$ , then an objective outlier test will be used to compare the atypical value to other values included in that calculation:
  - a. Transform all values in the calculation to the logarithmic domain.
  - b. Find the most extreme value from the arithmetic mean of the log transformed values and exclude that value from the dataset.
  - c. Calculate the lower and upper bounds of the range defined by the arithmetic mean  $\pm 3*SD$  of the remaining log-transformed values.
  - d. If the extreme value is within the range of arithmetic mean  $\pm 3*SD$ , then it is not an outlier and will be retained in the dataset.
  - e. If the extreme value is outside the range of arithmetic mean  $\pm 3*SD$ , then it is an outlier and will be excluded from analysis.

If the remaining dataset contains another atypical datum suspected to be an outlier and  $n \geq 6$  following the exclusion, then repeat step 2 above. This evaluation may be repeated as many times as necessary, excluding only one suspected outlier in each iteration, until all data remaining in the dataset fall within the range of arithmetic mean  $\pm 3*SD$  of the log-transformed values.

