#### Reporting of Excluded Values

Individual values excluded as outliers will be documented in the final CSR. Approval of the final CSR will connote approval of the exclusion.

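### The SAP's between-profile PK outlier rule both requires and does not require removal of a flagged value, and asks for no all-data summary beside it at the planned group size of about 10

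*SAP*

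**What the plan says.** SAP section 10.3.1 introduces its outlier procedure under Treatment of Outliers during PK Analysis. The introduction is permissive. It states that "Application of this procedure to all PK analyses is not a requirement", that "this procedure provides justification for exclusion of data when scientifically appropriate", and that the methodology "does not require that the value be excluded from analysis". It also bars use of the method to drop complete profiles.

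Under Data between Individual Profiles there are two branches:

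- Fewer than six values: "the dataset is too small to conduct a reliable range test". The remedy is "Data will be analyzed with and without the atypical value, and both sets of results will be reported".
- Six or more values: take logs, set aside the value furthest from the mean, and compute the mean ± 3 SD of the rest. If the value set aside falls outside, step 2(e) says "then it is an outlier and will be excluded from analysis". If a further suspect value remains, "This evaluation may be repeated as many times as necessary", provided at least six values are left.

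Under Reporting of Excluded Values, "Individual values excluded as outliers will be documented in the final CSR". SAP 10.3.2 lists the PK parameters and summarizes them by treatment. The General PK Parameter Rules require a footnote when an AUC(0-∞) value is left out of the summary. Under Data within an Individual Profile, a separate rule asks for results with and without a questionable data point in one participant's profile.

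**The concern.** Step 2(e) and the introduction give different consequences for the same event. An analyst who follows step 2(e) reports Cmax and AUC with the flagged value removed. One who follows the introduction may keep it. Both comply, and their summary tables differ.

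The SAP's own safeguard, showing both results, is switched off where the planned data lie. With 12 per cohort at 5:1, every dose group falls in the branch for six or more values.

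Cmax and AUC(0-∞) are the secondary endpoints, and their descriptive summaries are the whole analysis of them. If a genuine extreme value is removed, the table shows an understated CV and a shifted geometric mean. The all-data figures would have to be rebuilt from the listings.

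**Working it through.** **Inputs.** Group size: 12 × 5/6 = 10 donanemab participants per dose (SAP sections 5 and 8). Distribution: log-normal, as SAP 10.1 treats AUC and Cmax. Test: most extreme value against the mean ± 3 SD of the other 9, on the log scale. The true CV is not given; 30% is an assumption, with 15% to 40% as the range. The SAP states no false-flag rate, so there is no plan figure to reproduce.

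**What 3 SD means at n=10.** Let the other 9 values have SD 1 and let the tested value lie 3 from their mean.

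- Distance from the mean of all 10: 0.9 × 3 = 2.7.
- Sum of squares of all 10: 8 × 1 + 0.9 × 9 = 16.1, so the SD is √(16.1/9) = 1.337.
- Ratio: 2.7/1.337 = 2.02.

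The rule therefore flags any value more than about 2.02 ordinary SDs from the full-group mean.

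**Flag rate on clean data if every dataset is tested.** For one given value, its distance from the mean of the others in their SDs, divided by √(n/(n−1)), follows t with n−2 degrees of freedom.

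- 3/√(10/9) = 2.846.
- Two-sided probability on 8 df: 0.0216.
- Times 10 values: 0.216.

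The last line is strictly a bound on the chance of a flag; simulation gives the same 21.6% to rounding.

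**Effect of removing a genuine flagged value.** At the limit itself the log SD falls by the factor 1/1.337 = 0.75, so any removal cuts it by at least a quarter. Simulation (400,000 clean datasets per assumed CV, one removal) gives an average factor of 0.67 in flagged groups:

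| Assumed true CV | Mean geometric CV in flagged groups, before | After |
|---|---|---|
| 15% | 14.6% | 9.7% |
| 20% | 19.5% | 12.9% |
| 30% | 29.3% | 19.3% |
| 40% | 39.1% | 25.5% |

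At 30%, the geometric mean in flagged groups moves 7.0% on average in absolute terms. The mean signed log shift is 0.000 to three decimals, so there is no directional bias. For scale, the sampling SD of the geometric CV at n=10 and true CV 30% is 7.3 points; the fall within a flagged group is 29.3 − 19.3 = 10.0 points.

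**The case against.** The strongest reply is that the SAP does not prescribe testing every dataset. The introduction makes the procedure optional and ties exclusion to scientific judgement, and the test starts from a value already thought atypical. This stands. A reader might infer from 21.6% that about one dose group in five will lose a genuine value. The documents do not support that: the figure is an upper bound, and the realised rate is unknown.

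Second, the two sentences can be reconciled by treating the introduction as governing whether to run the test and step 2(e) as the outcome once it is run. This is a possible reading, but the introduction's last clause speaks of the identified value, not of the decision to test, and the SAP states no order of precedence.

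Third, a reader might infer that at six or more values nothing is ever shown both ways. That is too strong. The within-profile rule applies at any group size, and because Cmax is a single observed concentration, a doubtful Cmax could fall under it. It would not cover an extreme AUC from a wholly credible profile.

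Fourth, the consequence is limited. There is no hypothesis test, parameters are listed, exclusions are documented in the CSR, and AUC(0-∞) exclusions are footnoted. This also stands, and it rules out any suggestion of concealment. Documentation tells the reader that a value was removed, but it does not supply the all-data geometric mean and CV.

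**Conclusion.** The point holds at low severity. The SAP gives two instructions for a flagged value without saying which governs, and it requires no between-profile result with and without the value at the planned group size.

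The 3 SD limit gives weak protection at n=10. It amounts to about 2.02 ordinary SDs, with a false-flag rate of at most 21.6% per parameter and dose group, assuming log-normal data.

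The CV and geometric-mean effects in the table apply only when a genuine value has been removed, and their size depends on the assumed true CV. The harm is confined to the reported Cmax and AUC summaries. No test, sample-size claim or safety analysis is affected.

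**What to change.** In SAP 10.3.1:

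- In step 2(e), replace the instruction to exclude with wording that the value will be flagged as an outlier for potential exclusion, in line with the introduction.
- For six or more values, make the all-data summary of Cmax and AUC the main result, and report the summary without the flagged value beside it. This extends what step 1 already does for smaller sets.
- Make matching edits to the paragraph on repeating the test and to Reporting of Excluded Values, both of which now speak of excluded values.

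The cost is these text edits and one extra summary whenever a value is flagged. A truly erroneous value would stay in the main summary, with the result without it alongside. I do not propose a wider limit: it would flag fewer genuine values but also miss more real errors, and reporting both results avoids that trade-off.
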